Objectives	
Primary:
 
Determine if intra-pyloric botulinum toxin injection (Botox[®]) during a minimally invasive esophagectomy decreases postoperative occurrence of delayed gastric emptying. 
Secondary:
 
Determine if intra-pyloric botulinum toxin injection during a minimally invasive esophagectomy:
Reduces the number of repeat procedures for delayed gastric emptying within 90 days,Decreases time to oral intake meeting 100% of nutritional requirements,Reduces the incidence of pulmonary complications directly related to delayed gastric emptying,Reduces hospital length of stay related to delayed gastric emptying and,Increases patient quality of life.
Study Design	Double-arm, randomized, Phase II study
Target Accrual and Study Duration	A maximum of 50 evaluable patients at RPCI will be enrolled. Accrual is expected to take up to 6 years. Study participants will be followed for data collection for 90 days (routine post-esophagectomy follow-up care and surveillance, per standard of care). Data will be collected for 90 days on each patient.
Study Procedures	
Medical History, Pre-Existing Conditions (including smoking status and diabetes): Baseline
 
Disease Evaluation (Multidisciplinary evaluation and neoadjuvant therapy for esophageal carcinoma): Baseline
 
Hematology, Chemistry: Baseline, Postoperative course
 
Performance Status: Baseline
 
Physical Examination (including neurological examination, vital signs, and body weight): Baseline, Inpatient and Outpatient Postoperative Course
 
Electrocardiogram, Chest x-ray, and/or Pulmonary Function tests: At baseline, if clinically indicated.

	
Pregnancy test (urine): Baseline
 
Gastrograffin swallow or CT esophagram: Surgery to Discharge
 
Nuclear Medicine Emptying Study: Post Op Visit 2 (+/- 14 days)
 
Medical and Clinical Evaluation of Delayed Gastric Emptying: Inpatient and Outpatient Postoperative Course
 
Clinical Events of Interest and Adverse Events: During surgical procedure, Inpatient and Outpatient Postoperative Course
 
Nutrition Evaluation: At baseline, if indicated and, Inpatient and Outpatient Postoperative Course
 
EORTC QLQ OES18 Questionnaire: Outpatient postoperative course

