6.6 Outpatient Postoperative Follow-Up Visits

Study participants will be followed for data collection for 90 days (routine post-esophagectomy follow-up and surveillance, per standard of care). The following evaluations will be performed during the outpatient postoperative course, unless otherwise clinically indicated:

- In the postoperative period, patients return to office for outpatient follow-up approximately one to three weeks after discharge (“Postoperative Visit #1”). This visit is standard of care and can be scheduled per PI discretion. Physical exam and vital signs will be conducted at this visit. The dietician will assess oral intake, and supplemental tube feeds adjusted accordingly. Day until patient tolerates 75% and 100% of nutritional needs orally will be recorded as per nutritionist assessment.
- As a participant in this study, patients in both randomization groups will undergo a nuclear medicine emptying study. The nuclear medicine emptying study may occur within the window of Postoperative Visit #2 (\pm 14 days) to assess dynamic conduit function. This test can be extended beyond post-operative Visit #2 at PI’s discretion. Patients will be monitored for any symptoms of delayed gastric emptying during this time by questionnaire (See **Appendix C**), to determine if nuclear medicine study findings correlate with concurrent clinical symptoms.
 - Prior to the nuclear medicine emptying study, the patient must be fasting for at least 6 hours, including oral intake and any supplemental j-tube feeds. If the patient is a diabetic, the glucose level should be measured and less than 275 mg/dL within 2 hours of the study. Opiates must be held for 48 hours prior to the study. Patients should not be on any of the medications listed in **Appendix B** within the 48 hours prior to the study. Patients will remain in the nuclear medicine suite during this time, and will be required to sit upright, and may walk around the room. During the study, for the time between the images, the patients may be sitting, standing, or walking, but should remain in close proximity to the nuclear medicine facility.
- Post-surgical symptom evaluation based on clinical factors during the outpatient follow-up visits, and additionally by phone conversation between outpatient follow-up appointments if clinically indicated.

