- At Postoperative Visit #2, patients will be assessed for quality of life as measured by EORQLQ-C30 OES18 questionnaire (**Appendix D**). This will usually occur in the office around postoperative week six to eight. However, if the patient remains hospitalized during this time point, the questionnaire will be administered once between Postoperative Days 35-42.
- Concomitant medications: List any ongoing medications with dose changes, as applicable.
- Clinical Events of Interest and Adverse Events

Participants who are unavailable for follow-up evaluations should be classified as lost to follow-up for one of the following reasons:

- Lost to follow-up: For a participant to be considered lost to follow-up, the investigator must make two separate attempts to re-establish contact with the participant. The attempts to re-establish participant contact must be documented (e.g., certified letter).

- Death: Date and cause of death will be recorded for those participants who die within 30 days of surgery (telephone verification is acceptable).

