Medical evaluation (signs of pneumonia, aspiration)			X	X	X	
Nutrition evaluation ¹³	X (As indicated)		X ¹⁴	X	X	X (As indicated)
EORTC QLQ OES18 Questionnaire ¹⁰ See Appendix D					X	
Pregnancy Test ⁷ (Urine)	X					
Electrocardiogram, Chest x-ray, and/or Pulmonary Function tests	X (As indicated)					
Speech therapy evaluation			X (As indicated)			
Concomitant Medications	X ⁸	X	X	X	X	X
Clinical Events of Interest and AEs		X ⁹	X	X	X	X

Evaluation	Baseline ¹	Day of Surgery	Inpatient Postoperative Course ² (Surgery to Discharge)	Postoperative Visit #1 ³ ± 14 days	Postoperative Visit#2 ³ ± 14 days	End of Study phone call Day#90 (± 14 days)
Fasting glucose (for patients with diabetes)					X (As indicated)	

1 Baseline evaluations will be performed prior to the participant's scheduled minimally invasive esophagectomy and will be confirmed before surgery (Preoperative workup and multimodality therapy for esophageal cancer as standard of care at Roswell Park and based upon the NCCN guidelines for esophageal cancer. Refer to Section 6.2).

2 Patients will follow the standard of care postoperative pathway for minimally invasive esophagectomy.

3 Initial Standard of Care postoperative follow-up visit (Postoperative Visit #1) after hospital discharge, and then again at Postoperative Visit #2 if the postoperative course is uncomplicated. If complications arise, patients may be seen more often in follow-up. Patients will be followed for data collection for 90 days following surgery.

4 Vital signs (temperature, heart rate, respiratory rate, blood pressure), body weight and, height. Height collected at baseline only.

5 If indicated by the anesthesia pre-op assessment- Hematology: CBC with automated differentials (WBC, RBC, HGB, HCT, platelet, MCV, MCH, MCHC, % neutrophils, absolute neutrophils, % monocytes, absolute monocytes, % eosinophils, absolute eosinophils, % basophils, absolute basophils, % lymphocyte, absolute lymphocyte, platelet confirmation (as clinically indicated), and differential confirmation (as clinically indicated).

6 If indicated by the anesthesia pre-op assessment - Chemistry: CMP (chloride, CO₂, potassium, sodium, BUN, glucose, calcium, creatinine, total protein, albumin, total bilirubin, alkaline phosphatase, AST, ALT, A/G ratio, BUN/creatinine ratio, osmol (Calc), anion gap), as clinically indicated.

7 To be performed < 1 week prior to scheduled surgery,

8 Medications ongoing, or discontinued, within 1 week prior surgery.

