7.1.2 Drug Information- Botulinum toxin

OnabotulinumtoxinA (botulinum toxin type A, Botox[©]) inhibits the release of acetylcholine from nerve endings at neuromuscular junctions in the local muscle (10). Without the release of acetylcholine, neurotransmission between peripheral nerve endings and muscle fibers cannot occur, and the muscle becomes weak or paralyzed (10). The inhibitory effect of botulinum toxin is temporary, and muscle function recovers at 3 months after administration. The effect is not immediate, and rather occurs within 1-3 days.

With intramuscular injection at a dose of 100 units, botulinum toxin is not expected to be in contact with the peripheral blood (10). In rare instances, botulinum toxin may spread from the area of injection and produce symptoms consistent with botulinum toxin effects (13). These unanticipated symptoms may include asthenia, diplopia, ptosis, dysphagia, dysphonia, urinary incontinence, and breathing difficulties. These symptoms have been reported hours to weeks after injection.

Incidence of side-effects depends on injection site location. For example, patients treated with botulinum toxin injection into the sternocleidomastoid muscle for cervical dystonia are more likely to have the side-effects of swallowing difficulties, due to local diffusion. Swallowing and breathing difficulties may be life-threatening, and there have been reports of death (11). Patients with history of underlying conditions predisposing to muscle weakness have an increased risk of these side effects occurring (11). However, due to the nature of this study, patients with underlying muscle weakness are excluded from this study.

The maximum recommended dose of OnabotulinumtoxinA, regardless of the indication, is 400 units over three months (10). Cervical dystonia is treated with doses ranging from 198-300 units, divided among the affected muscle, with maximum dose 50 units per site. Our proposed dosage, 100 units in divided doses into the pyloric muscle, is within the range used among other high-volume esophagectomy centers (2, 3, 8, 9).

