9.1 Sample Size Determination

The sample size justification is based on the primary analysis. We consider a study design with a total sample of $n=50$ patients (randomly assigned in a 1:1 fashion to the Botox and non-Botox treatment arms) and an interim analysis at $n_1=30$. The performance of this study design and decision rules (described in the primary analysis) was assessed via simulation study.

If the true rates of delayed gastric emptying are 0.30 and 0.70 in the Botox and non-Botox treatment arms, then the study design achieves 85.0% power to detect a significant change in the delayed gastric emptying rates at a significance level of 0.05. The chance of stopping early for superiority is 42.8%, while the chance of stopping early due to inferiority is only 1.0%.

If the true rate of delayed gastric emptying is 0.70 in both treatment arms, then there is a 4.3% chance of falsely identifying the Botox arm as superior (observed type I error rate), a 0.9% chance of stopping early for superiority, and a 42.1% chance of stopping early for inferiority.

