9.2 Randomization

Patients will be randomized in a 1:1 fashion to the Botox and non-Botox treatment arms using a permuted block design. Participants will be stratified on the receipt of neoadjuvant chemoradiotherapy, smoking status, and diabetes. Participants will be randomized prior to the

minimally invasive esophagectomy, after signing consent for the surgical procedure. The randomization list will be developed by the Department of Biostatistics and Bioinformatics and provided to the study coordinator, who will then relay the information to the surgical team at the start of the procedure.

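### The primary emptying scan has no window counted from surgery, and the protocol contradicts itself on whether a scan after the Visit #2 window is allowed

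*Combined protocol and SAP*

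**What the plan says.** **Timing of the scan.** Sections 4.1, 6 and 6.6 set the nuclear medicine emptying study by Postoperative Visit #2 with a margin of 14 days either side. No section gives Visit #2 a postoperative day. The nearest statement, in the section 6.6 item on the quality-of-life form, is: "This will usually occur in the office around postoperative week six to eight". Visit #1 is counted from discharge (about one to three weeks after it). Sections 4.1 and 6.4 hold back discharge while there are clinical signs of delayed emptying. Table 2 footnote 3 has patients seen at Visit #1 "and then again at Postoperative Visit #2 if the postoperative course is uncomplicated. If complications arise, patients may be seen more often in follow-up". For a patient still in hospital, the quality-of-life form has a fallback of Days 35–42; the scan has none.

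**Late scans.** Section 4.2 replaces a patient who has no scan within 14 days of Visit #2. Section 6.6 says "This test can be extended beyond post-operative Visit #2", at the PI's discretion. Footnote 10 allows the same where the scan is contraindicated. Neither names a last day.

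**Drug effect and follow-up.** Section 7.1.2: "The inhibitory effect of botulinum toxin is temporary, and muscle function recovers at 3 months after administration". Section 1.1 gives a duration of three to five months. The synopsis says: "Data will be collected for 90 days on each patient".

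**Analysis.** Section 9.4 applies a one-sided Cochran-Mantel-Haenszel (CMH) test on the intent-to-treat principle. It has no window rule, adjustment or sensitivity analysis for time to scan. Section 4.1 blinds the patient and the radiologist but not the surgeon.

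**The concern.** The endpoint is one reading, taken once, of an organ whose function may change over the months after surgery and after a temporary drug effect. The reading should therefore be taken at a comparable time in every patient. Here the clock starts at a visit that follows discharge, and discharge can be delayed by the very condition being measured. Patients with a difficult course are the likeliest to be scanned off schedule.

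Two things are at stake. If late scans are counted, some may fall after the injected effect has gone or after data collection ends, and the contrast between arms is diluted. If late scans lead to replacement instead, patients leave the evaluable set because of what happened after randomization, which does not fit the intent-to-treat statement. Because the sections disagree, the choice between these could be made patient by patient. The documents do not say that whoever grants an extension is unaware of the arm.

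**Working it through.** **1. Where the usual window falls.** Weeks six to eight are days 42–56. With 14 days either side, 42 − 14 = 28 and 56 + 14 = 70, so the window is day 28–70. Taking 3 months as 90 days, it closes 20 days before the shorter stated duration. A scan on the usual schedule is not affected.

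**2. How a scan could pass day 90.** One route is an extension under 6.6 or footnote 10. The other is a late Visit #2. The quality-of-life fallback shows that the plan foresees patients in hospital up to day 42. Discharge then, with Visit #1 three weeks later, gives 42 + 21 = day 63. The gap from Visit #1 to Visit #2 is not stated. If it is g days, the scan window closes on day 63 + g + 14, which reaches day 90 once g is 13 or more.

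**3. The conflicting rules.**

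| Place | Scan outside Visit #2 ± 14 days |
|---|---|
| 4.1 | Not provided for; scan falls in the window |
| 4.2 | Patient is replaced |
| 6 | Exception if contraindicated, at the physician's discretion |
| 6.6 | Later scan allowed, PI's discretion, no last day |
| Table 2 footnote 10 | Later scan allowed if contraindicated, no last day |
| 9.4 | Intent-to-treat; silent on timing |

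The 4.2 limit is itself counted from Visit #2, so it fixes no day from surgery either.

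**4. Reproducing the design.** Inputs from sections 9.1, 9.2 and 9.4: "total sample of $n=50$ patients"; "an interim analysis at $n_1=30"; "Patients will be randomized in a 1:1 fashion"; rates 0.30 and 0.70; one-sided 0.05; bounds 0.011396 and 0.046533; stated power 85.0%.

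- Interim bound, O'Brien-Fleming-type spending at information fraction 30/50 = 0.6: 2[1 − Φ(1.960/√0.6)] = 2[1 − Φ(2.530)] = 0.011396, as stated. The final bound computes to 0.046528 against 0.046533.
- Power was simulated (8,000 runs) with a CMH test over 8 strata (three factors assumed binary), both bounds, and the stop when the estimated odds ratio exceeds 1. Stratum prevalences and block size are not in the plan. With 1:1 balance overall, power is 85.0% for assumed prevalences 0.8/0.5/0.2 and 84.0% for even strata. With blocks of 4 within strata it is 88–89%. The stated 85.0% is thus reproduced under plausible assumptions, though no single run matched every secondary figure.

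**5. Dilution (illustration).** Let a share f of Botox-arm scans revert fully to 0.70. The Botox rate is then 0.30(1 − f) + 0.70f = 0.30 + 0.40f.

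| f (of 25) | Botox rate | Difference from 0.70 | Power: 8 even strata, overall balance | Power: 8 even strata, blocks of 4 | Power: unstratified, exact two-stage |
|---|---|---|---|---|---|
| 0 | 0.30 | 40 points | 84.0% | 89.0% | 91.6% |
| 10% (2.5) | 0.34 | 36 points | 77.2% | 81.3% | 85.7% |
| 20% (5) | 0.38 | 32 points | 68.1% | 72.9% | 77.7% |
| 30% (7.5) | 0.42 | 28 points | 57.6% | 62.5% | 67.9% |

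The level depends on the variant. The loss is similar in all three: about 6–8, 14–16 and 24–27 points. Simulation error is at most about 0.6 points (one standard error, √(0.25/8000)).

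**6. Timing that differs by arm (illustration, no drug effect).** Suppose the delayed rate is 0.70 at the usual time and lower in late scans, in both arms. False-positive rates in the simulation with even strata and overall balance:

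- 20% late in each arm, late rate 0.50 (0.66 v 0.66): 4.8%.
- 30% late in Botox, 10% in control, late rate 0.50 (0.64 v 0.68): 8.7%.
- 40% v 10% late, late rate 0.30 (0.54 v 0.66): 19.8%.

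With more late scans in control (10% v 30%, late rate 0.50), the exact unstratified version gives 2.9%, against 5.3% with no late scans. The direction therefore depends on which arm is scanned later.

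**The case against.** The best defence is that the plan already contains a limit. Section 4.1 places the scan in the Visit #2 window, and 4.2 replaces anyone outside it, so a late scan need not reach the analysis at all. Some flexibility is also reasonable, because the scan requires fasting, a glucose limit and 48 hours without opiates. The usual window lies well inside the stated drug effect. All of this stands, and it confines the problem to a minority of patients whose number is unknown. It does not remove the conflict with 6.6 and footnote 10, and 4.2 gives no limit from surgery.

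A reader might infer four stronger things that the documents do not support:

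- *The scan may be postponed without limit.* That is 6.6 read alone. Section 4.2 says otherwise, and footnote 10 applies only where the scan is contraindicated.
- *Complications bring Visit #2 forward.* Footnote 3 allows more frequent visits. It does not say that an extra visit becomes Visit #2.
- *The effect is over at 3 months.* Section 7.1.2 supports this, but section 1.1 allows up to five months.
- *Late scanning must favour a null result.* Dilution does so if a real effect has worn off. Unequal timing can push either way, and equal late timing with no drug effect leaves the false-positive rate near nominal (4.8%).

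**Conclusion.** The point holds in a limited form and should be corrected. The primary scan has no window in days from surgery, its timing can depend on discharge and clinical course, and the sections conflict on whether a later scan is permitted or leads to replacement. The primary analysis does not settle the matter.

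The size cannot be fixed from the documents. The fall in power from about 84% to about 77, 68 or 58% assumes that 10, 20 or 30% of Botox-arm scans are late, that late scans are counted, and that the effect is then wholly lost. The false-positive figures assume a lower late-scan rate and unequal timing, neither of which the plan reports. They show what the wording leaves open and do not forecast what will happen. If nearly all scans fall in day 28–70, the effect on the result is small.

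**What to change.** 1. Define the scan window in days from surgery from the plan's own figures: target day 42–56, window day 28–70, whatever visits have taken place and including inpatients.
2. Give any extension a last permitted day, no later than the day-90 end of data collection. That is a ceiling, since it coincides with the shorter stated duration of effect.
3. Reconcile sections 4.1, 4.2, 6 and 6.6, Table 2 and footnote 10 so that they state the same window and the same exception.
4. In section 9.4, state one rule, the same in both arms, for how out-of-window and absent scans enter the intent-to-treat analysis. It should take the place of replacing patients for scan timing. The plan has no missing-outcome rule at present, so one must be written.
5. Record days from surgery to scan and report them by arm. If an analysis limited to day 28–70 scans is added, label it a non-randomised sensitivity analysis, because scan timing arises after randomization.

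The cost is protocol wording, one derived variable and one short analysis rule. The drawback is that a few patients not scanned by the last day become missing outcomes under the stated rule, so fewer than 50 observed scans may be available.

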6.7 End of Study Visit

- At day #90 (\pm 7 days), an end of study phone call will be conducted by the study coordinator. The purpose of this call is to inquire about any subsequent procedures the patient may have undergone related to delayed gastric emptying or esophagectomy, nutrition assessment to determine if the patient continues to require supplemental jejunal feeds, any persistent clinical symptoms of delayed gastric emptying, including any subsequent pneumonia, aspiration events, respiratory failure, nausea, vomiting, ability to eat solid food or drink liquids or having any trouble eating, early satiety, difficulty swallowing saliva, noticing bile or green staining on pillow while sleeping, experiencing acid indigestion or heartburn, or pain with eating, concomitant medications and Clinical Events of Interest and adverse events will be assessed. If the patient indicates continued use of tube feeds, the study coordinator will alert the dietitian to call the patient for further evaluation of the percentage of tube feeds versus oral intake. If the patient is no longer using jejunal feeds, the study coordinator will mark down “100% oral intake.

The schedule of procedures and observations for this study is summarized in **Table 2** below.

Table 2 Schedule of Procedures and Observations

Evaluation	Baseline ¹	Day of Surgery	Inpatient Postoperative Course ² (Surgery to Discharge)	Postoperative Visit #1 ³ ± 14 days	Postoperative Visit#2 ³ ± 14 days	End of Study phone call Day#90 (± 14 days)
Medical History, Pre-Existing Conditions (including smoking status, diabetes)	X					
ECOG Performance Status	X					
Multidisciplinary Evaluation and neoadjuvant therapy for esophageal carcinoma	X					
Physical Examination, including vital signs ⁴	X	X	X	X	X	
Hematology ⁵	X		X		X	
Chemistry ⁶	X		X		X	
Sign study informed consent, if eligible based on above factors	X					
Minimally invasive esophagectomy with or without pyloric drainage procedure		X				
Fasting glucose				X As indicated)		
Chest X-Ray, CT chest			X (As indicated)		X (As indicated)	

Evaluation	Baseline ¹	Day of Surgery	Inpatient Postoperative Course ² (Surgery to Discharge)	Postoperative Visit #1 ³ ± 14 days	Postoperative Visit#2 ³ ± 14 days	End of Study phone call Day#90 (± 14 days)
Gastrograffin swallow evaluation ¹² /CT esophagram			X ^{12a}			
Nuclear Medicine Emptying Study ^{10, 11}				X ¹¹ (Phone call prior to give instructions)		
Clinical Evaluation of Symptoms			X	X ¹¹	X	X
Medical evaluation (signs of pneumonia, aspiration)			X	X	X	
Nutrition evaluation ¹³	X (As indicated)		X ¹⁴	X	X	X (As indicated)
EORTC QLQ OES18 Questionnaire ¹⁰ See Appendix D					X	
Pregnancy Test ⁷ (Urine)	X					
Electrocardiogram, Chest x-ray, and/or Pulmonary Function tests	X (As indicated)					
Speech therapy evaluation			X (As indicated)			
Concomitant Medications	X ⁸	X	X	X	X	X
Clinical Events of Interest and AEs		X ⁹	X	X	X	X

Evaluation	Baseline ¹	Day of Surgery	Inpatient Postoperative Course ² (Surgery to Discharge)	Postoperative Visit #1 ³ ± 14 days	Postoperative Visit#2 ³ ± 14 days	End of Study phone call Day#90 (± 14 days)
Fasting glucose (for patients with diabetes)					X (As indicated)	

1 Baseline evaluations will be performed prior to the participant's scheduled minimally invasive esophagectomy and will be confirmed before surgery (Preoperative workup and multimodality therapy for esophageal cancer as standard of care at Roswell Park and based upon the NCCN guidelines for esophageal cancer. Refer to Section 6.2).

2 Patients will follow the standard of care postoperative pathway for minimally invasive esophagectomy.

3 Initial Standard of Care postoperative follow-up visit (Postoperative Visit #1) after hospital discharge, and then again at Postoperative Visit #2 if the postoperative course is uncomplicated. If complications arise, patients may be seen more often in follow-up. Patients will be followed for data collection for 90 days following surgery.

4 Vital signs (temperature, heart rate, respiratory rate, blood pressure), body weight and, height. Height collected at baseline only.

5 If indicated by the anesthesia pre-op assessment- Hematology: CBC with automated differentials (WBC, RBC, HGB, HCT, platelet, MCV, MCH, MCHC, % neutrophils, absolute neutrophils, % monocytes, absolute monocytes, % eosinophils, absolute eosinophils, % basophils, absolute basophils, % lymphocyte, absolute lymphocyte, platelet confirmation (as clinically indicated), and differential confirmation (as clinically indicated).

6 If indicated by the anesthesia pre-op assessment - Chemistry: CMP (chloride, CO₂, potassium, sodium, BUN, glucose, calcium, creatinine, total protein, albumin, total bilirubin, alkaline phosphatase, AST, ALT, A/G ratio, BUN/creatinine ratio, osmol (Calc), anion gap), as clinically indicated.

7 To be performed < 1 week prior to scheduled surgery,

8 Medications ongoing, or discontinued, within 1 week prior surgery.

9 To be recorded from the time of entry into the operating room until the post-operative follow up. Clinical Events of Interest and SAEs will be recorded in the electronic medical record, and found in the patient's operative note, anesthesia records, daily progress notes, consult notes, nutrition notes, and outpatient visit notes.

10 All procedures and evaluations listed are our post-esophagectomy standard of care at RPCI except for Nuclear Medicine Emptying Study, EORTC QLQ OES18 Questionnaire, and routine postoperative assessment by dietician. See Table 1 for definitions, section 4.1. If contraindicated per investigator's discretion, the nuclear medicine emptying study can be extended beyond post-operative Visit #2 at PI's discretion.

11 Evaluation as documented in Appendix C, Nuclear Medicine Questionnaire.

12 CT esophagram or gastrografin swallow.

12^a: As inpatient when clinically indicated.

13 Nutritional goals as defined in Section 6.4: Day tolerating 50% oral feeds, 75% oral feeds, 100% oral feeds.

14 Nutrition assessment will include a 24-hour calorie count on Postoperative Day #6 ±1 day.

